## 5. STUDY TREATMENTS

### 5.1. Allocation to Treatment

This study is open-label and all subjects will receive anidulafungin. The investigator's knowledge of the treatment should not influence the decision to enroll a particular subject or affect the order in which subjects are enrolled.

Eligible subjects will be considered enrolled into the study provided they have satisfied all entry criteria and a legal representative has provided consent. Subjects will be assigned a subject number at the time of screening. This identifying number will be retained for the subject throughout the duration of study participation and must be used on all correspondence and documentation.

The Principal Investigator is responsible for ensuring that the subject is eligible for the study.

All subjects will receive IV anidulafungin. For dosing purposes younger subjects must be weighed frequently (such as daily), but less frequently for older children as determined by the investigator. On Day 1, subject is to receive a loading dose of 3.0 mg/kg (not to exceed 200 mg). Subject is then to receive a daily maintenance dose of 1.5 mg/kg (not to exceed 100 mg) from Day 2 onwards.

After a minimum of 10 days of treatment with IV anidulafungin, subjects with microbiologically confirmed ICC may be switched to oral fluconazole (6 – 12 mg/kg/day, maximum 800 mg/day) provided that all of the following criteria are met:

- The subject is afebrile for at least 24 hour;
- The subject is able to tolerate oral medication;
- Documentation of two blood cultures negative for *Candida* spp separated by at least 24 hours;
- Eradication or presumed eradication of *Candida* sp. from any other sites of infection if identified at enrollment;
- The specific *Candida* isolate identified at study entry is susceptible (or presumed to be susceptible based on the species identified and local *Candida* sp. resistance patterns) to fluconazole;
- Signs and symptoms of *Candida* infection have improved such that the Investigator feels it is appropriate to switch to oral fluconazole.

Treatment will continue for a minimum duration of 14 days from the time of the last negative culture (defined as the second of two consecutive negative cultures, separated by at least 24 hours, following the last positive culture) and improvement of clinical signs and symptoms of candidemia or invasive candidiasis.

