### 5.2. Safety Analysis Set

This set consists of randomized subjects receive at least one dose of study medication. Subjects will be analyzed according to treatment received, ie, as treated.

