### **5.3.3. Safety ANALYSIS SET**

This set consists of all subjects who have received at least one dose of study medication.

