### **8.2.4. Safety Analyses**

No formal statistical analyses are planned for safety data. The safety and other endpoints detailed in [Section 6.2](#) will be listed and summarized in accordance with sponsor reporting standards, where the resulting data presentations will consist of subjects from the safety analysis set. Additionally, demography, medical history and adverse events will be presented separately for the MITT population.

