**8.2.4.5. Adverse Events**

All adverse events will be coded using the MedDRA dictionary. Frequencies of adverse events will be presented by system organ class, preferred term, age category, and severity level.

All causality treatment emergent adverse events will be presented using two different treatment groupings.

Firstly they will be presented for the one group where all adverse events are counted from start of study to end of follow-up period. This will provide an overall assessment of all adverse events in the study.

Secondly they will be split into time periods within the study:

- Those that occurred from start of study to end of treatment by anidulafungin, including up to end of follow-up period if no other antifungal was administered;
- Those adverse events that started after treatment with another antifungal up until the end of the follow-up period.

This will provide guidance as to which adverse events occurred during treatment with anidulafungin, as opposed to those that occurred during other therapies.

Treatment related treatment emergent adverse events will be presented in two ways:

- Firstly, for those that are considered to be caused by anidulafungin, providing a summary of treatment related adverse events;
- Secondly, for those that are caused by anidulafungin and/or fluconazole, providing a summary of adverse events for the anidulafungin plus fluconazole treatment regimen.

All causality treatment emergent adverse events and treatment related adverse events will also be summarized for the 6 subjects in the PK sub-study analysis set.

Adverse events and serious adverse events will be listed by subject for all age categories.

Adverse events leading to discontinuation or temporary dose reduction will be presented ([Discontinuation\(s\)](#) Section).

Adverse events will be reported in accordance with the sponsor reporting standards.

Additional tables summarizing adverse events that are considered to be potentially indicative of an infusion related reaction which occur during the anidulafungin infusion or within 60 minutes following completion of the anidulafungin infusion will be presented. The adverse event terms of interest are:

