Summary of Microbiological Response by Candida species by Age Group- MITT Population
Summary of Global Response According to Neutrophil Status at Baseline (ANC $\leq$ 500 and $>$ 500) - MITT Population
Summary of All Cause Mortality - Safety Population
Summary of All Cause Mortality - MITT Population
Analysis of time to death (All Causality) - Safety population
Analysis of time to death (All Causality) - MITT population
Discontinuations Due to Adverse Events - Safety Population
Temporary Discontinuations or Dose Reductions Due to Adverse Events
Treatment Emergent Adverse Events (All Causalities) - Safety Population
Treatment Emergent Adverse Events by System Organ Class (All Causalities) - Safety Population
Summary of Treatment-Emergent Risk Events (All Causalities) - Safety Population
Treatment Emergent Adverse Events (Treatment Related) - Safety Population
Treatment Emergent Adverse Events by System Organ Class (Treatment Related - Anidulafungin and Fluconazole) – Safety Population
Treatment Emergent Adverse Events by System Organ Class (Treatment Related - Anidulafungin) – Safety Population
Treatment-Emergent Adverse Events by System Organ Class (Treatment Related - Fluconazole) – Safety Population
Incidence and Severity of Treatment Emergent Adverse Events (All Causalities) - Safety Population
Incidence and Severity of Treatment Emergent Adverse Events (Treatment Related) - Safety Population
Incidence and Severity of Treatment Emergent Adverse Events (Treatment Related - Anidulafungin) - Safety Population
Incidence and Severity of Treatment Emergent Adverse Events (Treatment Related - Fluconazole) - Safety Population
Incidence and Severity of Treatment Emergent Adverse Events - by Risk (Safety Population)
Individual Listing of Deaths
Serious Adverse Events
Basic Results Disclosure for Treatment-Emergent Non Serious Adverse Events by System Organ Class and Preferred Term (All Causalities) For events having a frequency rate greater than 2
Basic Results Disclosure for Treatment Emergent Serious Adverse Events
Incidence of Laboratory Test Abnormalities (Without Regard to Baseline Abnormality)
Incidence of Laboratory Test Abnormalities (Normal Baseline)
Incidence of Laboratory Test Abnormalities (Abnormal Baseline)
Laboratory Test Data: Median Changes from Baseline to Last Observation
Frequency Table of First Fundoscopy - Right Eye
Frequency Table of First Fundoscopy - Left Eye
Frequency Table of Fundoscopy Changes - Right Eye

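### The two fluconazole-only adverse event tables are assigned to the whole Safety Population, and no fluconazole-exposed denominator is defined, so read as written their rates are diluted by the children who never switched

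*SAP*

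**What the plan says.** SAP Appendix 2, the output list for the interim analysis, contains two tables restricted to events judged related to fluconazole: "Treatment-Emergent Adverse Events by System Organ Class (Treatment Related - Fluconazole) – Safety Population" and "Incidence and Severity of Treatment Emergent Adverse Events (Treatment Related - Fluconazole) - Safety Population". Neither title carries any condition on having taken fluconazole.

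SAP 5.3.3 defines the population named in those titles: "This set consists of all subjects who have received at least one dose of study medication". SAP 8.2.4 applies it to safety outputs generally, "where the resulting data presentations will consist of subjects from the safety analysis set". The other definition of the set, in SAP 5.2, adds "Subjects will be analyzed according to treatment received, ie, as treated". No fluconazole-exposed set is defined in SAP section 5.

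Protocol 5.1 states that "This study is open-label and all subjects will receive anidulafungin". The same section makes oral fluconazole an option. Children with confirmed infection may switch after at least 10 days of IV treatment if a list of criteria is met. Children without confirmed infection may switch after at least 5 days.

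SAP 8.2.4.5 plans two treatment-related summaries, one for anidulafungin and one for the anidulafungin-plus-fluconazole regimen. It also splits all-causality events into two periods, the second being "Those adverse events that started after treatment with another antifungal up until the end of the follow-up period". No N is given for that second period.

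**The concern.** A child who never took fluconazole cannot have an event caused by it. If such children are counted in N, the percentage no longer estimates the risk of a fluconazole-related event in children given fluconazole. It mixes that risk with how often investigators chose to switch.

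Two consequences follow. The printed rate is too low for anyone judging tolerability of the oral step. Precision also looks better than it is, because N counts children who contribute no information on fluconazole. In addition, adverse events are shown by age category. A child must be able to tolerate oral medication to switch when infection is confirmed, so the switched share may differ between age groups. Differences between age columns could then reflect switching rather than risk.

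**Working it through.** **Figure to reproduce.** There is none. The documents give no expected fluconazole event rate, no switch share and no calculated sample size.

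**Inputs**
- Population of the two tables: Safety Population (SAP Appendix 2), meaning at least one dose of study medication (SAP 5.3.3).
- Exposure to anidulafungin: all subjects (Protocol 5.1).
- Exposure to fluconazole: optional and delayed (Protocol 5.1). The share is not stated, so it is an assumption, taken here from 20% to 80%.
- Interim size: SAP 3.1 triggers the interim at about 20 ± 2 subjects in each of the two older cohorts, so 2 × 18 = 36 to 2 × 22 = 44. I use 40.

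**Formula.** Let x be the number of children with a fluconazole-related event, N the Safety count, E the count with at least one fluconazole dose, and f = E/N. Then

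x/N = (x/E) × f,

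so the relative understatement is 1 − f. This is a proportion of the exposed rate, not a difference in percentage points.

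**Numbers.** With N = 40 and x = 2, the Safety-based rate is 2/40 = 5.0% (exact 95% interval 0.6 to 16.9%). Against that:

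| Assumed f | E | Rate among exposed, x/E (exact 95% interval) | Relative understatement, 1 − f |
|---|---|---|---|
| 0.2 | 8 | 25.0% (3.2 to 65.1%) | 80% |
| 0.4 | 16 | 12.5% (1.6 to 38.3%) | 60% |
| 0.5 | 20 | 10.0% (1.2 to 31.7%) | 50% |
| 0.6 | 24 | 8.3% (1.0 to 27.0%) | 40% |
| 0.8 | 32 | 6.25% (0.8 to 20.8%) | 20% |

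**No events observed.** The exact 95% upper limit is 8.8% on 40 subjects, 16.8% on 20 exposed and 36.9% on 8 exposed.

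The intervals only illustrate precision. SAP 8.1.1 plans Clopper-Pearson intervals for response and mortality rates, not for adverse events.

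**Tables not affected.** For anidulafungin, f = 1 because every subject receives it, so the understatement is zero. The combined-regimen table describes the whole treatment strategy, for which the Safety set is the right N.

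**The case against.** The strongest reply is that the SAP never writes out the denominator of any adverse event table. A population label names an analysis set, not necessarily a column N. SAP 8.2.4.5 defers presentation to sponsor reporting standards that are not in the documents, and SAP 5.2 says subjects are analysed as treated. A reader might infer that the documents prove division by the full Safety count. They do not. It is the natural reading of the titles, not a stated rule.

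That reply limits the point but does not remove it. This is a one-arm study (SAP 2.1.1) and SAP 5.4 marks treatment misallocation as not applicable. SAP 5.3.3 repeats the Safety definition without the as-treated sentence. Where Appendix 2 intends a restriction it puts it in the title, as in the laboratory tables split by normal or abnormal baseline and the sensitivity tables that drop indeterminate and missing responses. The fluconazole tables have no such restriction and carry the same population label as the anidulafungin tables beside them. If the denominator is instead merely unstated, the same sentence needs to be added.

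Other parts of the reply stand:
- The fluconazole-only tables appear only in the interim list. SAP 8.2.4.5 plans no fluconazole-only summary.
- The relevant N is about 36 to 44. The planned 60 in SAP 2.1.2 counts evaluable children with confirmed infection, so it is neither the interim N nor the Safety count.
- The exposed count should be recoverable, because SAP 8.2.4.8 splits treatment duration by age category and by IV versus oral. A reader should still not have to rebuild a safety rate from another table.
- For the period after another antifungal, Appendix 2 lists no table with that title, and an N of those who received another antifungal is at least as natural a reading. The gap there is an unstated N, not a demonstrated wrong one.

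**Conclusion.** The point holds for two interim tables. As written, they pool children who never received fluconazole, and the printed rate is the exposed rate times the share switched. The relative understatement is 1 minus that share: 80% to 20% over assumed shares of 20% to 80%, and 50% (5.0% against 10.0%) when 20 of 40 are exposed and 2 have an event. These sizes rest on the label being used as the denominator and on an assumed switch share.

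Two stronger readings are tempting and are not supported. A reader might infer that the primary safety result is biased. The primary objective concerns anidulafungin, to which every child is exposed, and its tables and the combined-regimen table are correct on the Safety set. A reader might also infer that correcting N makes the fluconazole and anidulafungin rates comparable. It does not. With confirmed infection, children switch only after at least 10 days of IV treatment and once afebrile, culture-negative and improved, so they are a selected group observed over a later window. The SAP plans no such comparison.

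**What to change.** In SAP Appendix 2 and 8.2.4.5:

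1. State that N for the fluconazole-related tables is Safety subjects with at least one dose of oral fluconazole.
2. State that N for the period starting after another antifungal is Safety subjects who received another antifungal.
3. Show both Ns by age category.
4. Keep the Safety set as N for all other adverse event tables, including the anidulafungin-related and combined-regimen ones.
5. Do not present the fluconazole and anidulafungin rates as directly comparable, and say why in a footnote.

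The cost is SAP wording and population flags derived from dosing and antifungal data already collected. The downside is a smaller N in those tables, which reflects how little information on fluconazole the study has.
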